6.2 Enrollment/Baseline

Children will not be considered enrolled in the study until they have received their first dose of vaccine. In the event that a volunteer is randomized but not enrolled on the day of first vaccination, they will be replaced with an eligible alternate.

Study Day 0 (Day of First Vaccination)

1. Verify that Informed Consent was obtained from the child's parent/guardian.
2. Verify that all applicable eligibility criteria have been met.
3. Perform abbreviated history (including concomitant medications) and physical exam, focusing on any acute complaints.
4. Obtain blood for hematology, biochemistry, anti-Na-GST-1 and anti-Na-APR-1 (M74) humoral and cellular immunology assays.
5. Obtain a urine sample for metabolomics study.
6. Record vital signs (blood pressure, a tympanic temperature, and heart rate).
7. Administer the vaccines.
8. Observe for at least 1 hour after vaccination to evaluate for immediate adverse reactions. During the 1-hour post-immunization wait period, study staff will discuss signs and symptoms of potential AEs with parent/guardian and child.

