1. Perform basic history and physical exam (including injection site), emphasizing examination of any acute complaints.
2. Record vital signs.
3. Obtain blood for anti-Na-GST-1 and anti-Na-APR-1 (M74) humoral and cellular immunology assays.
4. Obtain a urine sample for metabolomics study.

Study Day 70 (14 +/- 2 days after Second Vaccination)

1. Perform basic history and physical exam (including injection site), emphasizing examination of any acute complaints.
2. Record vital signs.
3. Obtain blood for hematology, biochemistry, anti-Na-GST-1 and anti-Na-APR-1 (M74) humoral and cellular immunology assays.
4. Obtain a urine sample for metabolomics study.

Study Day 84 (28 +/- 4 days after Second Vaccination)

1. Perform basic history and physical exam, emphasizing examination of any complaints.
2. Record vital signs.
3. Obtain blood for anti-Na-GST-1 and anti-Na-APR-1 (M74) humoral and cellular immunology assays.
4. Obtain a urine sample for metabolomics study.

Study Day 112 +/- 14 [Groups 1a, 2a, & 3a] or 180 [Groups 1b, 2b, & 3b]

(Day of Third Vaccination)

1. Perform basic history (including concomitant medications) and physical exam (including injection site), emphasizing examination of any acute complaints.
2. Obtain blood for hematology, biochemistry, anti-Na-GST-1 and anti-Na-APR-1 (M74) humoral and cellular immunology assays.
3. Obtain a urine sample for metabolomics study.
4. Record vital signs.
5. Administer the vaccine.
6. Observe for at least 1 hour after vaccination to evaluate for immediate adverse reactions.

Study Day 113/181 (1 day after Third Vaccination)

1. Perform basic history and physical exam (including injection site), emphasizing examination of any acute complaints.
2. Record vital signs.
3. Obtain a urine sample for metabolomics study.

Study Day 115/183 (3 +/- 1 days after Third Vaccination)

1. Perform basic history and physical exam (including injection site), emphasizing examination of any acute complaints.
2. Record vital signs.
3. Obtain a urine sample for metabolomics study.

Study Day 119/187 (7 +/- 1 days after Third Vaccination)

1. Perform basic history and physical exam (including injection site), emphasizing examination of any acute complaints.
2. Record vital signs.
3. Obtain blood for anti-Na-GST-1 and anti-Na-APR-1 (M74) humoral and cellular immunology assays.
4. Obtain a urine sample for metabolomics study.

Study Day 126/194 (14 +/- 2 days after Third Vaccination)

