7.2.2.3 Cellular Immunology Assays

Cytokine and chemokine assays will be performed on supernatants from cryopreserved PBMCs collected at various time points in the study, by separating PBMCs from whole blood and culturing cells with media only, the mitogen phytohemagglutinin, the antigens *Na-APR-1* (M74) or *Na-GST-*

1, and crude *N. americanus* antigens extracts (e.g., adult somatic crude antigen extract). Cytokines (e.g., IL-2, IL-4, IL-5, IL-10, TNF α , and IFN γ) will be quantified using Cytometric Bead Analysis kits of supernatants collected from PBMCs stimulated with Na-APR-1 (M74) or Na-GST-1 antigen for 48 and 72 hours *in vitro*. Chemokines (e.g., RANTES, MIP1a, MCP-1, and IP-10) will be quantified in supernatants using commercially available ELISA kits.

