10.2.2 Immunogenicity Review

The proportion of subjects with detectable anti-Na-GST-1 and anti-Na-APR-1 (M74) antibody responses, and the duration of these responses, will be summarized as descriptive measures. Geometric mean antibody responses will be compared between dose groups for each vaccine antigen with comparisons made by analysis of variance (ANOVA) tests and pair-wise comparisons by contrasts. Antibody responses will be measured at Days 0, 7, 14, 28, 56, 63, 70, 84, 112/180, 119/187, and 126/194 for interim analysis, with Days 140/208, 200/268, 290/358, and 380/448 added for final analysis.

To exploit the multiple measures of antibody within each subject, a longitudinal model may be built (if possible) to describe the antibody responses over time. The models will explore if there are any differences between those administered Na-APR-1 (M74)/Alhydrogel® co-administered Na-GST-1/Alhydrogel® and those administered the hepatitis B vaccine.

Summary statistics will be used to present exploratory study results of the cellular immune responses to Na-GST-1 and Na-APR-1 (M74) before and after immunization. To assess the changes in lymphocyte proliferative responses and cytokine/chemokine profiles over time, a generalized estimating equations model with robust standard errors will be constructed. When necessary, data reduction approaches will be used.

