10.3 Final Analysis Plan

The purpose of this trial is to estimate AE rates and patterns of immune response as well as to compare these rates and patterns when Na-GST-1/Alhydrogel® and Na-APR-1 (M74)/Alhydrogel® are administered separately or when they are co-administered.

This section briefly describes the statistical methods to be used; a detailed analytical plan will fully describe the methods. The analytical plan will discuss the planned approaches to missing data. Deviations from the original analytical plan will be thoroughly documented and reported to the Sponsor.

Descriptive and hypothesis-testing approaches will be used to meet the protocol objectives as stated in **Section 3**. Estimates will be presented with their 95% confidence intervals. Formal statistical tests, as outlined below, will be used to compare doses. Statistical tests will use a two-sided significance level of 5%.

Primary Objective: To evaluate the safety and reactogenicity of three different dose concentrations of *Na-APR-1* (M74)/Alhydrogel® co-administered with *Na-GST-1*/Alhydrogel® in healthy Gabonese children.

AEs will be coded according to Medical Dictionary of Regulatory Activities (MedDRA™) preferred terms. The frequency, severity, and relationship of AEs per each dose of *Na-APR-1* (M74)/Alhydrogel® and *Na-GST-1*/Alhydrogel® compared to Hepatitis B vaccine will be presented in tabular form using the MedDRA™ coded term and organized by MedDRA™ System, Organ, and Class (SOC) designations.

- The frequency of immediate, systemic, and local injection site AEs will be summarized by SOC and preferred term.
- Line listings of clinical and laboratory AEs classified as immediate (within the first 60 minutes), systemic, and local will be displayed in tables stratified by vaccine (i.e., hookworm vs. Hepatitis B vaccines) dose of *Na-APR-1* (M74)/Alhydrogel® and *Na-GST-1*/Alhydrogel®.
- AEs will be summarized by severity and relationship to vaccine by individuals and dose of *Na-GST-1* and *Na-APR-1* (M74).
- The frequency of vaccine-related SAEs will be tallied as well as summarized by body system, by vaccine and dose.

Primary Outcome Measures:

The following summary parameters will be evaluated for each vaccine (hookworm vs. Hepatitis B) and dose of *Na-APR-1* (M74) co-administered with *Na-GST-1*:

1. Frequency of solicited injection site and systemic reactogenicity, graded by severity, on the day of each study vaccination through 14 days after each study vaccination.

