- a. The proportion of subjects with detectable anti-*Na-GST-1* and anti-*Na-APR-1* (M74) IgG1-4 subclass responses will be summarized at each time point as a descriptive measure.
- b. IgG1-4 subclass antibody levels will be displayed graphically by study group using notched box plots at each time point.
- c. Geometric mean antibody responses will be compared between vaccine and dose groups. Comparisons between groups will be made by a one-way analysis of variance (ANOVA) with pair-wise comparisons between groups made by contrasts.
- d. A longitudinal model will be built to describe each of the antibody isotype levels over time for each of IgG1-IgG4. Using a longitudinal panel model, differences in antibody isotype levels by dose of *Na-APR-1* (M74) and *Na-GST-1* will be explored. This will take account of the correlation between measurements on the same participant.

Exploratory Objective 1: To assess the cellular immune responses to the *Na-GST-1* and *Na-APR-1* (M74) antigens following vaccination.

The following assays will be performed to assess the cellular immune responses to vaccination with *Na-APR-1* (M74) +/- *Na-GST-1*:

- a. Lymphocyte proliferative responses to *in vitro* stimulation with *Na-GST-1* or *Na-APR-1* (M74).
- b. Cytokine and chemokine production *in vitro* in response to stimulation with *Na-GST-1* or *Na-APR-1* (M74).
- c. Changes in *in vivo* PBMC subpopulations as determined by flow cytometry.
- d. A longitudinal panel analysis will examine for trends over time.

Exploratory Objective 2: To assess the impact of co-administered *Na-GST-1* and *Na-APR-1* (M74) on the production of memory B cells specific for each antigen.

- a. The percentage of specific memory B cells will be displayed graphically by study group at each time point.
- b. Two separate longitudinal panel analyses will test the null hypothesis that average percentages for each of memory B cells are the same in groups over time. This will take account of the correlation between measurements on the same participant.
- c. Mann-Whitney tests will assess the null hypothesis that cytokine levels are the same in the groups at the primary time point two weeks after final vaccination.

Exploratory Objective 3: To assess the production of memory B cells specific for each vaccine antigen compared to metabolomic changes before and after vaccination.

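### The two-week cytokine comparison tests the post-vaccination level alone and leaves out the Day 0 value of the same assay

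*Combined protocol and SAP*

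**What the plan says.** Section 10.3, Exploratory Objective 2, item (c), applies Mann-Whitney tests to the null hypothesis that "cytokine levels are the same in the groups at the primary time point two weeks after final vaccination". It does not say which groups are compared, and it names no baseline value, change score or stratification.

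The Day 0 instructions in Section 6.2 read: "Obtain blood for hematology, biochemistry, anti-Na-GST-1 and anti-Na-APR-1 (M74) humoral and cellular immunology assays". Section 6.3 repeats the cellular sampling at Day 126/194, 14 days after the third dose, and both appendix schedules mark cellular assays at Day 0 and at that visit. Section 2.2.4 lists cellular responses on vaccination days. Section 7.2.2.3 is less specific on timing: "Cytokine and chemokine assays will be performed on supernatants from cryopreserved PBMCs collected at various time points in the study".

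Two other analyses cover cytokines. Section 10.2.2 plans summaries before and after immunization and a model for "cytokine/chemokine profiles over time, a generalized estimating equations model with robust standard errors will be constructed". Section 10.3, Exploratory Objective 1, which includes cytokine production, adds: "A longitudinal panel analysis will examine for trends over time". Tests are two-sided at 5%.

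**The concern.** A two-sample Mann-Whitney test has no place for a covariate. Whatever varied between children before the first dose stays in the noise. That variation may be appreciable. The children are long-term residents of an endemic area (Section 4.1), a local survey found 51% of 210 people hookworm-positive (Section 1.1.2), and children found infected at screening may enrol after treatment (Sections 4.1 and 6.1). The cohorts will therefore probably mix recently infected and uninfected children.

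There is also a question of bias. Randomisation is between hookworm vaccine and hepatitis B within a cohort. Dose follows the order in which cohorts are enrolled, and schedule follows enrolment order within a cohort (first ten, then last ten; Section 4.3.2). If the undefined groups in item (c) include dose cohorts, a difference that existed before vaccination can be reported as a dose effect.

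**Working it through.** **The plan's own figures.** No power, SD, effect size or correlation is given for cytokines. The only sample-size figures are probabilities of seeing at least one event, 1 − (1 − p)^N. For N = 20 and p = 10% this is 1 − 0.9^20 = 87.84%, as printed, and all 15 table cells reproduce. They do not bear on this test.

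**Inputs from the documents.** Each cohort has 16 hookworm-vaccine and 4 hepatitis B children. Pooled over three cohorts that is 48 and 12; within one cohort and schedule it is 8 and 2.

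**Assumed inputs.** Correlation ρ between Day 0 and two-week values: 0.3, 0.5 or 0.7. True difference: 0.8 or 1.0 SD. Continuous data, no dropout.

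**Approximation.** Adjustment multiplies residual variance by 1 − ρ². At ρ = 0.5 that is 0.75, a 25% cut. Adjusted power is Φ((z + 1.96)/√(1 − ρ²) − 1.96), where z is the normal quantile of unadjusted power. At ρ = 0.5:
- from 30%: (−0.524 + 1.96)/0.866 − 1.96 = −0.30, so 38.1% (+8.1 points)
- from 50%: 1.96/0.866 − 1.96 = 0.30, so 61.9% (+11.9)
- from 80%: (0.842 + 1.96)/0.866 − 1.96 = 1.28, so 89.9% (+9.9)

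The gain peaks at +12.4 near 60% and falls to +2.0 from 10%. At ρ = 0.3, starting from 50%, it is +3.8.

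**Simulation at ρ = 0.5** (4,000 trials per setting, Monte Carlo error of one power about √(0.25/4,000) = 0.8 points). Mann-Whitney on the two-week value against normal-score ANCOVA on Day 0, without a cohort term:

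| Contrast | 0.8 SD | 1.0 SD |
|---|---|---|
| 12 v 48, pooled | 66.4% to 77.9% (+11.5) | 83.4% to 92.4% (+9.0) |
| 16 v 16, dose v dose | 56.4% to 68.0% (+11.6) | 74.5% to 85.1% (+10.6) |
| 12 v 16, pooled controls v one dose | 49.4% to 59.9% (+10.5) | 65.8% to 77.2% (+11.4) |
| 4 v 16, within cohort | 26.0% to 31.1% (+5.1) | 36.8% to 44.2% (+7.4) |

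Repeat runs for 12 v 48 and 16 v 16 spread over about 9 to 14 points. For 2 v 8 the gain was +0.4 to +2.4. The 4 v 16 figures are against an exact Mann-Whitney test. A gain of 9 to 12 also appears for that contrast, but roughly half of it arises because the comparison test is conservative at that size. Type I error of the adjusted test was 4.8% to 5.6% in the three larger contrasts.

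**Other correlations.** At ρ = 0.3 the gain is about 1 to 6 points across contrasts (about 1 for 4 v 16). At ρ = 0.7 it is about 15 to 27 in the larger contrasts.

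**Undetectable values.** With 60% of Day 0 and 30% of unshifted post-dose values at a detection floor (assumed), the gain at ρ = 0.5 is +7 to +9 for 12 v 48 and +8 to +10 for 16 v 16. At ρ = 0.3 it is about +3.

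**Source of the gain.** Normal scores without Day 0 add only about 2 points over Mann-Whitney; the rest comes from baseline. A Mann-Whitney test on change from baseline gains almost nothing at ρ = 0.5, within about 1 point of the post-dose value alone.

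**False positives in a dose contrast.** Take 16 v 16, no vaccine effect and a 0.5 SD Day 0 difference between cohorts. The expected two-week difference is 0.5ρ and its standard error is √(2/16) = 0.354.
- ρ = 0.5: 0.25/0.354 = 0.71, and Φ(0.71 − 1.96) + Φ(−0.71 − 1.96) is about 11%
- ρ = 0.7: 0.35/0.354 = 0.99, giving about 17%

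These are z-test values. Simulated Mann-Whitney rejection was 10% and 15%, against about 5% after adjustment.

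**The case against.** The strongest reply is that little depends on this. The endpoint is exploratory, Section 10.1 says the trial is not powered for group differences, and the interim report that guides the next step (Section 14.4) uses safety and IgG. Section 10.3 describes itself as brief and defers to a detailed analytical plan. An unadjusted Mann-Whitney test is valid for the randomised contrast. All of this stands and keeps the priority low. It does not remove the point, because item (c) is specific: test, value and time are all named, and the baseline is left out.

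A second reply is that the plan already models cytokines longitudinally. A reader might infer from item (c) that baseline is ignored altogether. The documents do not support that: the estimating-equations model and the Objective 1 panel use repeated measures and could include Day 0. But one is described as assessing change and the other trends, and neither is specified as a Day 0-adjusted group contrast at two weeks.

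A third reply is that the size rests on chosen inputs. That is right. Day 0 and the endpoint lie 126 or 194 days apart, and nothing in the documents makes a correlation of 0.5 likelier than 0.3.

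**Conclusion.** The concern holds in a limited form. Item (c) leaves out a baseline that the schedule provides for, and no other planned analysis is stated to give the adjusted comparison at that time point.

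A reader might infer a single loss of roughly ten points. That is not supportable. It applies to 12 v 48, 16 v 16 and 12 v 16 at an assumed correlation of 0.5 and mid-range power. It does not carry over to the within-cohort 4 v 16 or 2 v 8 contrasts, or to a correlation of 0.3, and it shrinks in the larger contrasts if many Day 0 values are undetectable. Correlation, effect size and the groups being compared are all assumptions.

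A reader might also infer that adjustment makes dose comparisons safe. It reduces error from differences present at Day 0, but dose remains non-randomised, and period or batch effects arising after Day 0 remain.

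**What to change.** Reword item (c) in the detailed analytical plan:
- **Groups.** Name pooled hookworm vaccine versus hepatitis B, stratified by cohort, as the randomised contrast. Label dose contrasts as non-randomised.
- **Main test.** Rank-based ANCOVA on normal scores of the two-week level, with group as the factor and normal scores of the Day 0 level of the same cytokine under the same stimulus as covariate.
- **Sensitivity.** Keep Mann-Whitney on the two-week level. Do not substitute a simple change score.
- **Links.** State how item (c) relates to the estimating-equations model and the Objective 1 panel, and confirm that Day 0 samples are assayed for cytokines.

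No new blood sample is needed. The covariate costs one degree of freedom and the three-cohort stratification two more. A child without usable Day 0 cells would drop out of the adjusted test unless a missing-baseline rule, such as an indicator, is written in beforehand.

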11 SOURCE DOCUMENTS AND ACCESS TO SOURCE DATA/DOCUMENTS

Complete source documentation (clinical evaluations and test results) will be collected for every child participant for the duration of the study, with supplementary documents (laboratory test reports, supplementary hospital or medical records, etc.) forming part of the source documentation. Case Report Forms (CRFs) will be used to record study-specific data for enrolled subjects, and study-specific data may be entered directly onto CRFs: in these cases, the documents will be both source and CRF. The Principal Investigator will be responsible for the accuracy and completeness of the data reported in the CRFs and the source documents. Data reported in the CRFs that is derived from source documents should be consistent with source documents and the discrepancies should be explained.

12 QUALITY CONTROL AND QUALITY ASSURANCE

The investigational site is responsible for conducting routine quality assurance and quality control activities to internally monitor study progress and protocol compliance. The PI will provide direct access to all trial-related sites, source data/documents, and reports for the purpose of monitoring and auditing by the sponsor, and inspection by local and regulatory authorities. The PI will ensure all study personnel are appropriately trained and applicable documentation is maintained on site.

Clinical monitors will verify that the clinical trial is conducted and data are generated, documented (recorded), and reported in compliance with the protocol, ICH/GCP guidelines, and the applicable regulatory requirements. Clinical monitoring reports will be submitted to the Sponsor.

The data management vendor will implement quality control procedures beginning with the data entry system and generate data quality control checks that will be run on the database. Any missing data or data anomalies will be communicated to the site(s) for clarification and resolution.

13 ETHICS/PROTECTION OF HUMAN SUBJECTS

The study will be conducted according to fundamental ethical principles including: The principle of respect for human dignity and the principles of non-exploitation, non-discrimination and non-instrumentalisation. The principle of individual autonomy (entailing the giving of free and informed consent, and respect for privacy and confidentiality of personal data); The principle of justice (the equitable distribution of burdens and benefits of research). The principle of beneficence and non-maleficence, namely with regard to the improvement and protection of health; and, the principle of proportionality (including that research methods are necessary to the aims pursued and that no alternative more acceptable methods are available).

13.1 Ethical Standards

The study will be conducted according to: the Declaration of Helsinki (amended in 2008); CIOMS (Council for International Organizations of Medical Sciences) International Ethical Guidelines for Biomedical Research Involving Human Subjects (2002); International Conference on Harmonisation of Technical Requirements for Registration of Pharmaceuticals for Human Use (ICH) (1996) Guideline for good clinical practice E6 (R1); and, the US Code of Federal Regulations (Protection of Human Subjects [21 CFR 50], Institutional Review Boards [21 CFR 56], and Obligations of Clinical Investigators [21 CFR 312]).

13.2 Institutional Review Boards

The investigators will be responsible for obtaining full IRB approvals for the study from the local and national IRB in Gabon. Before the start of the study, the appropriate documents (including the protocol, Investigator's Brochures, and informed consent form) will be submitted to the IRBs. The IRBs will be informed by the Investigator of any new information that may adversely affect the safety of the subjects or the conduct of the study, an annual update and/or request for re-approval, and when the study has been completed.

13.3 Informed Consent and Assent Process

The principles of informed consent in the current edition of the Declaration of Helsinki will be implemented and informed consent obtained in accordance with ICH guidelines. A community meeting will be held to provide volunteers with an overview of the clinical trial and study procedures, and to answer questions in an open forum. This group meeting will be followed by individual informed consent sessions with each interested parent or legal guardian of a potential child participant. During the individual session a member of the study team will read the consent form together with the parent/guardian, regardless of whether or not the parent/guardian is illiterate. The study team member will explain why the parent/guardian's child is being invited to participate in the study and will clarify all of the parent/guardian's questions. Throughout the informed consent process, parents/guardians will be encouraged to ask questions, and if they wish, to discuss the study with family or community members prior to making a decision.

Parents/guardians agreeing to have their child participate in the study will first provide written informed consent and take a true/false comprehension questionnaire. The questionnaire is administered orally in the case of illiterate individuals, and for both written and oral questionnaires study staff will use incorrect answers to identify aspects of the study that require clarification and focus on those areas of the informed consent form for further review with the parent/guardian. All questionnaire questions must be answered correctly, and the informed consent form signed, prior to study screening and enrollment of the child. Parents/guardians unable to read will place an imprint of their finger in the place of a signature; in addition, an independent witness, who is not a member of the study team, will sign the consent form to attest that the informed consent form was read to the parent/guardian, the parent/guardian's questions were answered, and the parent/guardian answered all comprehension questions correctly. The original signed informed consent form for each parent/guardian will be maintained as part of their child's study records. A copy of the informed consent form will be provided to every child's parent/guardian.

The child assent form will also be introduced to the participants because it is directly addressed to the child where procedures related to the study are explained to them in simple language. The child will have to assent and sign. However, if the child is unable to read, an independent witness, who is not a member of the study team will sign the form.

